## 8.4 Restrictions during the study

The following life-style behavior patterns are forbidden during the study:

- All recreational drugs (i.e., the use of any illegal drugs, or the use of legal drugs for recreational purposes).
- Smoking and the consumption of alcoholic drinks are prohibited during the study.

For restrictions on concomitant medications and other forms of treatment, see Section 8.3.

## 8.5 Blinding

The main period of the study will be conducted in a double-blind fashion. All vials containing study medication (active or placebo) will have the same appearance. The identity of individual IP will remain unknown to the investigator, medical staff, all subjects, their caregivers and other study staff (excluding the external unblinded biostatistician). All other individuals involved in the study (e.g. clinical study manager, medical expert, study biostatistician) will remain blinded.

An independent DMC will assess subject safety data throughout the study (see Section 12.4.7.3). Special care will be exercised in the selection of DMC members in order to safeguard the study team from unblinding. Procedures for the evaluation of safety data and unblinding will be documented in writing. Details of DMC members and the committee's charter are provided separately.

## 8.5.1 *Emergency envelopes*

The computer randomization program (see Section 8.2.1) also will be used to prepare a complete set of sealed emergency envelopes. In an emergency, these envelopes will allow unblinding of the treatment received by an individual subject while maintaining the overall study blind. The set of envelopes will be sent to

, Germany) to be kept there for emergency unblinding if necessary.

At the end of the study, all emergency envelopes are to be returned to the sponsor's quality management department. Any opened emergency envelope must be returned bearing the date and reason for opening.

Any other emergency unblinding will be done through the IWRS.

## 8.5.2 Unblinding procedures

The blind will not be broken until the blind data review meeting has convened, the statistical analysis plan [SAP] has been finalized, and the database has been closed. After the blind is broken, the statistical analysis of results will proceed, which will be documented according to GCP.

The DMC will be semi-blinded with respect to treatment group comparisons based on frequency tables ("semi-blinded" means here that tables will only contain labeled treatment-group information such as "Treatment A" and "Treatment B"). Subject data

Merz Pharmaceuticals GmbH MRZ60201 3091 1

listings will not contain any treatment-group information; thus, the DMC will remain blinded in respect of the treatment administered to individual subjects. To ensure blinding of the sponsor's study-team members and of the staff at the sites, these persons will not participate in the closed sessions of the DMC meetings and will not have access to the semi-blinded data prepared for the DMC. An electronic version of the semi-blinded treatment allocation ("Treatment A" and "Treatment B") will be transferred from the randomization officer to the DMC biostatistician, who will be responsible for the preparation of the tables and listings for the DMC meetings and will not be part of the study team. The DMC may require knowing the actual treatment for single subjects in order to evaluate the safety information of AESIs and SAEs received from the study to early identify signals and to give advice. The biostatistician of the DMC will also receive IWRS access and a password enabling him/her to break the blinding code of subjects via this system. The DMC biostatistician is responsible for the safekeeping of the password. If safety concerns arise that require the unblinding of a subject by the DMC, then the DMC should confer with Merz before performing unblinding of the subject by IWRS. Detailed procedures for unblinding in any case of safety concern are laid down in the DMC charter.

The investigator will remain blinded throughout the study except in cases where unblinding is required: In the event of an SAE that requires further therapeutic decisions depending on the knowledge of the treatment group, the investigator will use the IWRS for unblinding. The sponsor will be notified through the IWRS. Additionally, the Corporate Product Safety department will be able to unblind subjects by means of the IWRS.

Furthermore, PharmOlam will also receive IWRS access and a password for regulatory unblinding for reporting suspected unexpected serious adverse reactions to regulatory authorities and IEC(s)/IRB(s).

# **9** STUDY ASSESSMENTS AND VISIT SCHEDULE

## 9.1 Assessments

## 9.1.1 Clinical evaluations

#### 9.1.1.1 General assessments and screening

After consent and assent has been obtained, at the screening visit the subject's demographic data, medical history and all previous (i.e., administered within the past year for BoNT products or 45 days for all other medications), current and concomitant medications and treatments planned during the study will be recorded (see Section 8.3). A review of this information will aid the investigator in assessing whether the subject should be enrolled. Other data will be collected as required, including information obtained from a physical examination (which must include the chest, to ensure there is no previous evidence of aspiration), a neurological examination and vital signs (see below). For children suffering of cerebral palsy (CP) the severity of CP will be assessed by the Gross Motor Function Classification System (GMFCS) at baseline. Dental examination by a dentist needs to be performed during the screening period (allowing the investigator to review the dental examination report and dental exclusion criteria at baseline visit the latest). Counseling of parents and subjects may take place according to need and mental capacity, at the investigator's discretion. In case if the subject is not eligible (due to any temporarily limited condition e.g. short term infection of airways) at the baseline visit he/she will be considered to fail screening. Rescreening of this particular subject is allowed to be performed subsequently to the resolution of the temporary condition. In this case a new screening number needs to be generated and all screening assessments need to be he repeated.

The following vital signs will be examined as scheduled in the overview of study activities (Table 6): heart rate and systolic and diastolic blood pressure (after 5 min. in a recumbent position); temperature. Body height will be measured with a stadiometer, and body weight (with the subject in underwear and not wearing shoes) will also be measured.

#### 9.1.1.2 *Efficacy assessments*

The following efficacy assessments will be used to compare the efficacy of the active treatment (NT 201) with that of placebo. Details of these assessments are given in the appendices to this protocol Appendix 16.3.

• Unstimulated salivary flow rate [uSFR] (weighing of two absorptive swabs soaked with saliva over five minutes; procedure repeated once after 30 minutes [±5 minutes]) for all randomized subjects.

• Global Impression of Change Scale [GICS] of functioning as a result of treatment from last injection on a 7-point scale by carer/parent(s) and subject in a combined rating.

#### 9.1.1.3 Safety assessments

The following assessments will be used to assess the safety of the study treatment:

- Adverse events [AEs] including e.g. adverse events of special interest [AESIs] (see also Section 10.3.) and serious adverse events [SAEs].
- Vital signs (blood pressure, heart rate, body temperature).
- Body weight, height.
- Clinical chemistry and hematology as possible for the age group of the child/adolescent (for details see Section 9.1.2).
- Urinary pregnancy test (in female subjects >12 years of age or with a history of menarche, i.e. the first menstrual bleeding only) prior to every injection session and at the end-of-study visit.
- Dental and oral examination by a dentist during the screening period until baseline, in Week 4, at the final visit of the main period V6 (Week 16), at V10 and the end-ofstudy visit, in terms of adverse events: findings indicating a worsening of the subject's dental / oral condition since screening/baseline are to be recorded as adverse events (Appendix 16.4).

Each subject will be observed at the investigation site by the site personal and supervised by a physician for at least two hours after administration of the injections, to detect and control any bleeding, pain, swelling or other adverse events resulting from the injections into the salivary glands and any side effects of the applied analgesia or sedation.

• Emergency pediatric equipment and fast access to pediatric intensive-care facilities must be available in the event of an adverse reaction related to study drug administration, sedation or general anesthetic. Latently developing iatrogenic botulism due to toxin spread needs to be treated in a pediatric intensive-care facility.

Merz Pharmaceuti	cals G	mbH
MRZ60201	3091	1

To monitor potential spread of toxin, subjects, carer and parent(s) (as appropriate) will be actively questioned about the occurrence of AESIs at every visit after every injection session of investigational product (for details see Section 10.3). AESIs are to be reported to the responsible CRO within 24 hours (see reporting procedure in Section 10.2). Any adult responsible for the child's care will be given (a) contact card(s) with emergency instructions for the prompt reporting of adverse events.

All subjects for whom AEs are reported, whether these are considered related to the use of investigational product or not, will be monitored carefully until the AE has resolved or stabilized, or until the final visit of this study (i.e. 16 weeks after the last injection of the IP).

# 9.1.2 Laboratory evaluations

## 9.1.2.1 Clinical and research laboratory evaluations

Blood and urine will be sampled for standard laboratory assessments and for antibodies against BoNT according to the schedule set out in Table 6. For hematological measurements 1.2 mL blood will be drawn into an EDTA tube, for clinico-chemical assessments 1.2 mL blood will be drawn into a serum tube and for antibodies against BoNT testing 19.9 mL blood will be drawn into 3 serum tubes for subjects  $\geq$ 30 kg BW. The total blood volume required for this study will be 47.0 mL over 72 weeks (details in Table 5 and Section 9.1.6).

In order to minimize distress and bruising, only qualified staff, experienced in pediatric venipuncture, will perform the blood draw as follows:

- All children will be offered local anesthesia (e.g., using lidocaine plaster such as EMLA or lidocaine or Ametop cream).
- Children will always have a loved one present to comfort them (if they want) and be distracted during the blood sampling as necessary.
- Depending on IEC/IRB advice and local rules, we suggest that only two attempts should be made for research-only sampling. Should the participant become acutely and inconsolably distressed during or before the blood draw the procedure must stop immediately and the subject must be withdrawn from the sampling.
- Blood samples will be kept to a minimum, particularly for the younger children.

## 9.1.2.2 Clinical chemistry, hematology and pregnancy tests

Safety laboratory assessments will include the values listed in Table 4 below.

Clinical Chemistry:	Alanine aminotransferase	Glucose
	Albumin	γ-Glutamyltransferase
	Alkaline phosphatase	Lipase
	Amylase, total *	Potassium
	Aspartate aminotransferase	Protein total
	Bilirubin, total †	Sodium
	Calcium	Triglycerides
	Chloride	Thyroid-stimulating hormone
	Cholesterol, total	Urea / Blood urea nitrogen
	Creatine kinase	Uric acid
	Creatinine	
Hematology:	Hematocrit, hemoglobin, red bl (MCH, MCV, MCHC)	ood cell count and derived parameter
	White blood cell count	
	Differential count (automated c count, percentage)	ount, percentage and absolute; manual
	Platelet count	
Pregnancy test:	β-HCG Human chorionic gona bearing potential only) in urine specified).	dotropin, beta form (in females of child- (at visits where pregnancy testing is

#### Table 4: Standard safety laboratory values

\* If total amylase is elevated, then pancreatic amylase will also be measured

† If total bilirubin is increased, then indirect bilirubin will also be measured.

## 9.1.2.3 Antibodies against Botulinum toxin

To detect antibodies against *Botulinum* toxin in study subjects the fluorescence immunoassay [FIA] and the hemidiaphragm assay [HDA] will be used.

Blood will be sampled for analysis of antibodies against BoNT for subjects with  $\geq$ 30 kg BW. For children with <30 kg BW no blood samples for analysis of antibodies against BoNT will be taken. Blood amounts will be taken according to the weight group of the subject in context of all blood withdrawals during the study (Section 9.1.7). For subjects with  $\geq$ 30 kg BW first blood samples are taken at baseline (V2). Subsequent antibody tests after repeated IP exposure will be performed for subjects with  $\geq$ 30 kg BW only at the end-of-study visit (V18; alternatively, if preferred, at V17).

The serum amount necessary for FIA-AB is 1.5 mL and 4.5 mL for HDA. To yield the required serum amount the estimated blood amount is 4.9 mL for FIA-AB and 15 mL (2x7.5 mL) for HDA. Sample work-up at the study site includes preparation of serum by centrifugation at room temperature and transfer into provided tubes. Serum samples should preferably be stored at -20°C ( $\pm$ 5°C) but must be within a range of -5°C to -90°C until frozen shipment to the analyzing laboratory.
Blood samples will be screened using the FIA-AB that detects antibodies against BoNT A in human serum. FIA-AB detects binding to specific BoNT epitopes and allows the identification of sera that react with the toxin, but the FIA-AB is not capable to discriminate between neutralizing and non-neutralizing antibodies [Goschel 1997].

Samples that are positive in the FIA-AB will be tested using the validated mouse ex vivo HDA. The HDA is the most sensitive functional assay (sensitivity <0.5 mU/mL) currently available [Sesardic 2004]. To spare animals, the assay is performed only if the FIA-AB is positive.

### 9.1.3 Pharmacodynamics

Not applicable.

### 9.1.4 *Pharmacokinetics*

Not applicable.

### 9.1.5 *Pharmacogenetics*

Not applicable.

#### 9.1.6 Table of blood volume

Blood samples will be taken for general safety testing (hematological and clinicochemical assessments) and also for additional measurements of antibodies against BoNT.

Laboratory evaluations will be performed as possible for the age group of the subject. The bulletin of the World Health Organization published a recent literature review on the blood sample volumes in child health research [Howie 2011]. The author concludes that blood sample volume limits ranging from 1-5% of total blood volume [TBV] within 24 hours and up to 10% of total blood volume over eight weeks were consistent with minimal risk to healthy children as far as limited evidence available may support any risk evaluation. However, lower limits for sick children seem advisable.

Per individual, the trial-related blood loss (including any losses in the maneuver) should not exceed 3% of the total blood volume during a period of four weeks and should not exceed 1% at any single time. The total volume of blood is estimated at 80–90 ml/kg body weight; 3% is 2.4 ml blood per kg body weight [European Medicines Agency (EMA) 2008].

In this study, the lower limits mentioned for relevant age groups and weight classes in literature [European Medicines Agency (EMA) 2008] will be applied. Blood sample collection for clinical chemistry and hematology will be restricted in frequency and

volume. Limits will be set by the following assumption on the TBV and restrictions on maximum blood volumes withdrawn per time period:

TBV= 80 mL/kg body weight

Maximum blood volume in any withdrawal: 1% of TBV

Maximum blood volume over 12 weeks: 3% of TBV

A central laboratory capable of handling properly the relatively smaller volumes of samples (as compared to those usually obtained from adult subjects) will perform the analyses.

The following blood volumes are necessary to result in sufficient serum volumes for the respective tests:

•	Hematology (EDTA tube):	1.2 mL
•	Clinical chemistry (serum tube):	1.2 mL
•	Fluorescence immunoassay [FIA]:	4.9 mL blood (1.5 mL serum)
•	Hemidiaphragm assay [HDA]:	15.0 mL blood(4.5 mL serum)

Note that for clinical chemistry the same procedure for blood sampling is always to be followed, irrespective of which laboratory values are to be measured at the visit in question. Details of the procedures, including possible local anesthesia, are given in Section 9.1.2

Table 5 shows the maximum amounts of blood that will be required and the calculated maximum total amount of blood to be drawn during the study.

Visit	Blood volume withdrawn		
	Hematology *	Clinical chemistry †	Antibody tests †#
Screening	1.2 ml	1.2 ml	
Visit 2			19.9 ml
Visit 6	1.2 ml	1.2 ml	
Visit 18	1.2 ml	1.2 ml	19.9 ml
Total volume drawn:		$7.2 \text{ ml} (47.0 \text{ ml}^{\#})$	

Table 5: **Blood volumes required** 

\* To be collected in an EDTA tube (Section 9.1.2). † To be collected in a serum tube (Section 9.1.2). # Only for subjects with  $\geq$  30 kg BW (Section 9.1.2.3).

## 9.1.7 Specimen preparation, handling, storage, and shipping

This study does not involve the retention of any biological samples. The only samples taken will be blood and urine for safety testing (the latter for on-site pregnancy tests only). These will be analyzed at the central laboratory without retention of material.

## 9.2 Visit schedule

The purpose of the screening visit is to determine the subject's eligibility for study participation. The subject will be notified of any new diagnosis of an abnormal medical condition during the screening process, and will be referred for appropriate care. The screening evaluation must be completed 7–28 days (Table 6) before the baseline visit.

The baseline visit, at which the final decision on inclusion, the randomization (subjects aged 6-17 years only) of the subject and the administration of the first study treatment are performed, is defined as Day 1.

During the study, subjects will receive NT 201 (or, in the main period, matching placebo [subjects aged 6-17 years only]) at the beginning of each 16-week injection cycle. The visit schedules with study activities are shown in Table 6. For each study visit a time window is allowed, as detailed in Table 6 and described in Section 6.1.2.

The final study visit will take place after a total of  $64 \pm 8$  weeks, at the end of the fourth injection cycle. Since this will be as long as  $16 \pm 2$  weeks after the last administration of NT 201, no further visit for safety follow-up is planned.

At the physician's discretion, the final visit of each study injection cycle can be advanced by up to two weeks (e.g., if the physician considers earlier repeated treatment/assessment to be advisable) or postponed by up to two weeks (in the converse situation).

Unscheduled visits may be required in the case of premature discontinuation of study treatment. In this case, a final assessment (the end-of-study visit) will be performed. If additional safety follow-up is necessary after this assessment, subjects may be contacted by telephone or assessed in the clinic, depending on the nature of the follow-up required.

Table 6:Schedule of study tests, procedures and clinic visits

SOP/245/EN - CLINICAL STUDY PROTOCOL Version 2.0 Version 16-JUN-2016

Merz Pharmaceuticals GmbH

# **10** SAFETY ASSESSMENTS

### **10.1** Definition of an adverse event

An AE is any untoward medical occurrence in a subject administered a pharmaceutical product that does not necessarily have a causal relationship with the treatment. Thus, an AE can be any unfavorable and unintended sign, symptom, or disease (including intercurrent illness); deterioration of a pre-existing illness; accident; any suspected drug reaction; or a clinically relevant change of laboratory values whether or not considered related to the IP and/or study treatment.

Changes in efficacy variables (e.g., subject-reported outcome variables [questionnaires and scales] during the course of the study) need not be documented as AEs, because these changes will be recorded as efficacy variables. Elective treatments planned before screening and which are documented in the subject's source data are usually not regarded as AEs.

The period of observation for AEs extends from the time when the informed consent form was signed until the subject's final study visit. Any medical occurrence between the time when the informed consent form is signed and the first intake of study medication is an AE and has to be documented in the subject's file and in the eCRF AE report form.

Non-serious AEs will not be followed up after the final study visit (i.e.,  $16 \pm 2$  weeks after the last administration of NT 201), which will take place after a total of  $64 \pm 8$  weeks, at the end of the fourth injection cycle. In cases of study participation discontinuation the final visit takes place  $16 \pm 2$  weeks after the last administration of NT 201, after which no further visit for safety follow-up is considered necessary (see Section 9.2).

Pre-existing conditions that do not worsen during the course of the study are not reportable as AEs. To determine whether a condition has worsened, it is compared to the condition of the subject at screening. Abnormal clinically relevant laboratory values obtained during the subject's screening period will only meet AE criteria if newly detected.

Incidental findings of abnormal laboratory values will be reported to the investigator immediately so that the subject can promptly be referred for treatment and care.

Data pertaining to AEs will be collected during each study visit based on the subject's spontaneous description, through investigator inquiry, or discovered in the course of examinations done during the visit. The investigator will assess and record any AE in detail in the subject file and on the eCRF AE report page. The following information must be recorded:

• AE diagnosis or main symptom.

- Date of onset.
- Date of worsening.
- Intensity (maximum observed; see Section 10.1.1).
- Causal relationship (not related, related).
- Serious (yes or no).
- Outcome (see Section 10.1.3).
- Action taken with IP (see Section 10.1.3).
- Whether the AE led to discontinuation of the study (yes or no).
- Date of resolution (and time, if applicable).

After completion of all scheduled visit assessments the investigator must document any AEs arising from these assessments.

In the case of an SAE or an AESI (alert term, as defined in Section 10.3), the investigator is also to complete an SAE report form or AESI report form and report the event to the sponsor immediately, as described in Section 10.2.

Conduct in the unlikely event of overdose with NT 201 is described in Section 8.2.6.

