#### **End-of-study visit**

This will be the same as the end-of-cycle visit for the fourth injection cycle (above). Subjects who withdraw, or are withdrawn, prematurely from the study will be requested to attend for this final examination.

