Subjects who are withdrawn from the study because of AEs will be treated by standard clinical methods and will be followed up until (and including) the last scheduled visit of the injection cycle in which they were withdrawn or until 28 days after the onset of the adverse event, whichever date is the later. All pertinent information concerning the AE will be documented in the subject's hospital medical file as well as in the eCRF AE report form.

Following a subject's withdrawal, a final examination should be performed for safety reasons if parents/carers are willing to bring the child for the visit. The investigator is required to make every effort to contact subjects lost to follow-up, and all such efforts are to be documented in the subject's hospital medical file (e.g., times and dates of telephone contact, copies of letters).

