<sup>4 According to ICH E2A, CPMP/ICH/377/95: "Medical and scientific judgment should be exercised in deciding whether expedited reporting is appropriate in other situations, such as important medical events that may not be immediately life-threatening or result in death or hospitalization but may jeopardize the patient/subject or may require intervention to prevent one of the other outcomes listed in the definition above. These should also usually be considered serious. Examples of such events are intensive treatment in an emergency room or at home for allergic bronchospasm; blood dyscrasias or convulsions that do not result in hospitalization; or development of drug dependency or drug abuse."

The address for SAE reporting is:

The investigator must supply further supporting information within 3 days of knowledge of the SAE, and a detailed SAE description is an integral part of this supporting information. Follow-up reports should be sent without delay to the CRO as an SAE report form (marked as a "follow-up" report) and accompanied by appropriate supporting documentation (e.g., hospital reports). The SAE has to be followed up until the SAE is resolved/recovered or a plausible explanation is available. These SAEs will be followedup only in the Corporate Product Safety database after final SAE reconciliation is completed.

SAEs occurring after the end of the observational period need only be reported if the investigator considers the event to be related to the IP. These reports generally will not be entered into the study database.

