#### Adverse Events

AEs will be coded according to the Medical Dictionary for Regulatory Activities (MedDRA) (version in effect when the database is closed).

TEAEs of MP are defined as AEs with onset or worsening after the first injection of NT 201 or Placebo up to and before first injection of the extension period or - in case of discontinuation before second injection – up to and including 16 weeks after first injection of NT 201 or Placebo or date of last study visit, whichever is later. AEs starting in the MP and not having resolved at the final visit of MP (V6) will be followed and further documented in the extension period.

TEAEs of OLEX are defined as AEs with onset or worsening after the first injection of OLEX up to and including 16 weeks after last injection or the date of last study visit, whichever is later.

A detailed description of the rules to be used for the classification of TEAEs can be found in Appendix 1. If an AE worsens between start and end of this AE it will be considered as new AE starting with the date of the worsening. In this case the imputation of end dates within episodes of the same AE will be done by setting the end date/end time to start date/start time of the consecutive worsening record.

In detail missing or partially missing start and stop dates of an AE will be imputed as follows for the calculation of the duration of an AE:

Page 26 of 46

- if start time is missing and date is given and not equal to first exposure date in MP or OLEX, set time to 00:00, else if date is equal to first exposure date in MP or OLEX set time to time of first exposure in MP or OLEX, if given (else 00:00), respectively
- if start time is missing and date is given and equal to the subsequent exposure date in OLEX (e.g. 2nd injection in OLEX), set time to time of the subsequent exposure, if given (else 00:00)
- if start date/time is completely missing and end date is not after or equal to first exposure of MP: no imputation.
- if start date/time is (partially) missing and end date is after or equal first exposure in MP or missing:
  - $\circ$  only start day is missing, but month and year same as first exposure in MP or OLEX: set day and time to day and time of first exposure, else set day to 1 and time to 00:00
  - Start day and month are missing, but year is the same as year of first exposure in the MP (which is ≠ year of first exposure in OLEX): set day, month, time to day, month, time of first exposure in the MP

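### Protocol Sections 9.2 and 10.1 time a withdrawn child's final visit differently, so AE collection can end before the SAP's 16-week TEAE window closes

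*Protocol*

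**What the plan says.** **When AE collection ends.** Protocol Section 10.1: "The period of observation for AEs extends from the time when the informed consent form was signed until the subject's final study visit".

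**When the final visit falls for a child who leaves early.**
- Section 9.2: "Unscheduled visits may be required in the case of premature discontinuation of study treatment". It continues: "In this case, a final assessment (the end-of-study visit) will be performed". No week is given, and further safety contact by telephone or in clinic is optional.
- Section 10.1: "In cases of study participation discontinuation the final visit takes place" 16 ± 2 weeks after the last administration of NT 201, with a reference to Section 9.2.
- Section 6.1.2, under the end-of-study visit: "Subjects who withdraw, or are withdrawn, prematurely from the study will be requested to attend for this final examination". No date is given.
- Section 7.5.1: "Following a subject's withdrawal, a final examination should be performed for safety reasons if parents/carers are willing to bring the child for the visit". No date is given here either. The same section follows children withdrawn because of AEs to the cycle's last scheduled visit, or to 28 days after AE onset if that is later.

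**What happens to later SAEs.** Under Section 10.2, an SAE after the observational period has to be reported only if the investigator considers it related. On such reports the section says: "These reports generally will not be entered into the study database". The observational period is not defined there.

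**What is analysed.** The TEAE window in SAP Section 7.5 for the extension runs "up to and including 16 weeks after last injection or the date of last study visit, whichever is later". For a child who discontinues before the second injection, the main-period window likewise runs to at least 16 weeks after the first injection. Protocol Section 12.4.5 instead stops at the last recorded contact for early leavers. SAP Section 8, which lists changes to the planned analyses, does not mention this difference.

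**The concern.** The collection period is tied to a visit whose timing depends on which section the site reads, while the analysis window is tied to the injection. A site that follows Section 9.2 can do the end-of-study assessment when a child leaves, and AE observation then ends under Section 10.1. AESI questions are asked at visits, so with no further visit there is no further planned questioning. The child stays in the safety evaluation set, and any weeks left in the SAP window count as if they were event-free.

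Section 10.1 does not fully settle the matter, even on its own terms. Its anchor is the last administration of NT 201, and a placebo child who leaves in the main period has had none. Read literally, the rule gives that child no date, and the main period is where the controlled safety comparison is made.

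Occurrence of TEAEs is the primary safety variable. Protocol Section 6.2 describes an effect that develops over about two weeks and wanes after 8–12 weeks, so the uncollected weeks can include weeks in which the toxin is still active.

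**Working it through.** **1. The plan's own timing figures.** Each cycle lasts 16 ± 2 weeks (Protocol Section 6.1.2).
- Four cycles: 4 × 16 = 64 weeks, with a range of 4 × 14 = 56 to 4 × 18 = 72. This matches Section 8.2.4.
- Main period: screening of 1–4 weeks plus 14–18 weeks = 15–22 weeks. This matches Section 6.1.1.

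The schedule is internally consistent. The difficulty is confined to early leavers.

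**2. Uncollected part of the SAP window.** Let t be the week of the final visit, counted from the last injection. Assume no contact after it. The SAP window closes at week 16 or at the last visit, whichever comes later, so

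gap = max(16, t) − t.

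The documents give no value of t for early leavers under Section 9.2, so a range is shown:

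| Final visit (week t) | Gap (weeks) | Share of 16 weeks |
|---|---|---|
| 2 | 14 | 88% |
| 4 | 12 | 75% |
| 8 | 8 | 50% |
| 12 | 4 | 25% |
| 14 | 2 | 12.5% |
| 16 or later | 0 | 0% |

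As t approaches 0, the limit is just under 16 weeks.

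**3. The same formula under Section 10.1.** With t between 14 and 18, the gap is 16 − 14 = 2 weeks at most, and 0 from week 16 on.

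**4. Who can be affected.**
- *Withdrawn because of an AE:* followed at least to the cycle's last scheduled visit under Section 7.5.1, so the gap is small.
- *Not re-injected because the extension criteria are unmet (Section 7.4):* the decision falls at about weeks 14–18, so the gap is at most 2 weeks.
- *Leaving mid-cycle for another reason:* the full Section 9.2 gap can apply.
- *Consent withdrawn:* later collection may not be possible under any rule.

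**5. Whether early last visits are foreseen.** The SAP provides for them. In Section 7.6, a child who does not enter the extension counts as a main-period completer only if the last visit is on day 95 or later. A discontinued cycle is measured to the last available visit, and cycles shorter than 14 weeks have their own category.

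**The case against.** The strongest reply is that the sections can be read together, with Section 9.2 naming the visit and Section 10.1 dating it. Section 10.1 cites Section 9.2, and Section 9.1.1.3 also describes the final visit as 16 weeks after the last injection of investigational product. On that reading the gap is 0–2 weeks. The protocol also requires efforts to contact children lost to follow-up and allows later telephone contact. The SAP's longer window discards no recorded event.

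Much of this stands. A reader might infer that the protocol sets the final visit at the moment of discontinuation. No section says so; Section 9.2 ties the visit to the discontinuation but gives no date. The body of Table 6 could not be read in the copy available, so any timing it gives is not considered here.

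The harmonised reading still does not remove the problem. When Section 10.1 points to Section 9.2 for early leavers, it points to text that describes an unscheduled visit and discretionary follow-up. It gives no literal date for a placebo child. Efforts to reach lost children and optional calls are not planned AE collection to a fixed week.

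**Conclusion.** The conflict is real, and the end of AE collection depends on how it is read. Under Section 9.2, a child leaving mid-cycle for a reason other than an AE can have 16 − t weeks of the SAP window uncollected. Under Section 10.1 the gap is at most 2 weeks. TEAE, AESI and SAE incidences can therefore be understated for such children. This assumes that the site uses the Section 9.2 reading and makes no later contact.

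Three stronger conclusions are tempting but not supported:
- *That 12–14 weeks are typically lost.* That figure needs a final visit at weeks 4–2, and the documents give no withdrawal times.
- *That a known share of children is affected.* Protocol Section 12.1.1 includes 144 to secure 100 followed for a year, which implies an allowance of (144 − 100)/144 = 30.6%. This is a planning margin over a year in the NT 201 group. It is not a rate of mid-cycle, non-AE withdrawal.
- *That the controlled comparison is biased in a known direction.* Section 12.4.7.1 expects different reasons for missing data in the two arms, but it concerns efficacy data and supposes comparable percentages. The extra NT 201 losses it foresees are from AEs, and those children are followed to the end of the cycle.

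**What to change.** Reconcile Protocol Sections 6.1.2, 7.5.1, 9.2, 10.1 and 10.2 so that the end of AE collection no longer depends on when the final examination is done:
- For every withdrawn child, whatever the reason, collect AEs, AESIs and SAEs to 16 weeks after the last injection of NT 201 or placebo, unless consent to contact is withdrawn. Sections 9.1.1.3 and 10.1 and the SAP already use 16 weeks. Naming placebo gives both arms a date.
- Close collection with a planned contact, for example the telephone contact that Section 9.2 already allows.
- In Section 10.2, define the observational period as the same 16 weeks, so that all SAEs within it are reported and entered in the study database.
- Align the TEAE windows in Protocol Section 12.4.5 and SAP Section 7.5, and record the change in SAP Section 8.

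The cost is wording in these sections and one contact per early leaver. Reported AE incidences may rise slightly. The change concerns data collection only and touches no dose or treatment rule.
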